## 8.2. Adverse Events of Special Interest Analyses

A comprehensive list based on clinical review will be used to identify each type of event. AEs of special interest will be manually-selected before unblinding at patient-level (i.e. following case-by-case review by members of the Safety Review Team (SRT) including representatives from the local Japan team) and not at preferred term level. The details of the planned displays are provided in [Appendix 10: List of Data Displays](#).

Endpoint / Parameter/ Display Type	Absolute		
	Summary		Individual
	T	F	L
AEs of special interest 			
On-Therapy AEs of special interest	Y		Y
Post-therapy AEs of special interest	Y		Y

**NOTES:**

- T = Table, F = Figures, L = Listings, Y = Yes display generated, SOC = System Organ Class, PT = Preferred Term.
- Summary = Represents TF related to any summaries (i.e. descriptive statistics) of the observed raw data.
- Individual = Represents FL related to any displays of individual subject observed raw data.

[1] Refer to Section [15.6.4](#)

### 8.2.1. Planned Adverse Events of Special Interest Analyses Displays

- **AEs of Special Interest (AESIs)**

*AEs of Special Interest*

The number and percentage of subjects reporting at least one AESI will be provided by treatment group. These events will be summarized by each AESI term (See Section [15.6.4](#)). On-therapy and post-therapy AESIs will be summarized separately.

## 8.3. Clinical Laboratory Analyses

Laboratory evaluations including the analyses of Chemistry/ Hematology/Other Laboratory tests, and liver function tests will be based on GSK Core Data Standards. The details of the planned displays are in [Appendix 10: List of Data Displays](#).

Endpoint / Parameter/ Display Type	Absolute			Change from BL		
	Summary	Individual		Summary	Individual	
	T	F	L	T	F	L
Chemistry						
Chemistry Values by Visit	Y		Y	Y		
Percent Change from Baseline in Lipid Parameters  (total cholesterol, LDL cholesterol, HDL cholesterol, and LDL/HDL cholesterol ratio) by Visit			Y	Y	Y	
Worst Case Chemistry Results Relative to Normal Range Post-Baseline Relative to Baseline	Y					
Worst Case Chemistry Results Relative to PCI Criteria Post-Baseline Relative to Baseline	Y					
Hematology						
Hematology Values by Visit	Y		Y	Y		
Worst Case Hematology Results Relative to Normal Range Post-Baseline Relative to Baseline	Y					
Worst Case Hematology Results Relative to PCI Criteria Post-Baseline Relative to Baseline	Y					
Iron Parameters						
Iron Values by Visit 	Y		Y	Y		
Worst Case Iron Results Relative to Normal Range Post-Baseline Relative to Baseline	Y					
Worst Case Iron Results Relative to PCI Criteria Post-Baseline Relative to Baseline	Y					
Other Laboratory Tests 						
Other Laboratory Values by Visit	Y		Y	Y		
Worst Case Other Laboratory Results Relative to Normal Range Post-Baseline Relative to Baseline	Y					
Worst Case Other Laboratory Results Relative to PCI Criteria Post-Baseline Relative to Baseline	Y					
Hepatobiliary (Liver)						
Liver Monitoring/Stopping Event Reporting	Y					
Hepatobiliary Laboratory Abnormalities	Y					
Medical Conditions for Subjects with Liver Stopping Events			Y			
Substance Use for Subjects with Liver Stopping Events			Y			
Scatter Plot of Maximum vs. Baseline for ALT		Y				
Scatter Plot of Maximum ALT vs Maximum Total Bilirubin		Y				
All Laboratory						
All Laboratory Data for Subjects with any Value of Potential Clinical Concern/PCI			Y			
Laboratory Values of PCI			Y			

**NOTES:**

- T = Table, F = Figures, L = Listings, Y = Yes display generated, PCI = Potential Clinical Importance
- Summary = Represents TFL related to any summaries (i.e. descriptive statistics) of the observed raw data.
- Individual = Represents FL related to any displays of individual subject observed raw data.

[1] Lipid parameters will be log-transformed and the percent change from baseline will be reported.

[2] Transferrin and UIBC will be included for this summary and other iron parameters will be provided as efficacy endpoints.

[3] Only iPTH will be collected as other laboratory tests.

### 8.3.1. Planned Clinical Laboratory Analyses Displays

LDL/HDL cholesterol ratio will be derived from LDL and HDL cholesterol (see Section 15.6.4), and handled as one of chemistry laboratory tests and lipid parameters.

- ***Chemistry/Hematology/Iron Parameter/Other Laboratory Tests***

*Clinical Laboratory Values by Visit*

The values will be summarized using mean, standard deviation, median, minimum, and maximum at each assessment visit and baseline by treatment group. Chemistry, hematology, iron parameter, and other laboratory values will be summarized separately.

*Percent Change from Baseline in Lipid Parameters*

Lipid parameters (including LDL/HDL cholesterol ratio) will be log-transformed and the percent change from baseline will be reported. The percent change from baseline in each lipid parameter, including baseline values, will be summarized using geometric mean, 95% CI, minimum, median, and maximum at each assessment visit by treatment group. In baseline values, the coefficient of variation will also be provided.

*Clinical Laboratory Changes from Baseline by Visit*

The values will be summarized using mean, standard deviation, median, minimum, and maximum at each assessment visit. Change from baseline in chemistry (excluding LDL/HDL cholesterol ratio), hematology, iron parameter, and other laboratory will be summarized separately.

*Worst Case Laboratory Results Relative to Normal Range/PCI Criteria Post-Baseline Relative to Baseline*

The number of subjects with worst case laboratory results relative to normal range/potential clinical importance (PCI) criteria which are post-baseline relative to baseline, including unscheduled assessments, will be summarized by test and category by treatment group. Summaries for normal range and PCI will be provided separately. The categories for normal range are: To Low, To Normal or No Change, To High; the categories for PCI criteria are: To Low, To w/in Range or No Change, To High. The categorization is determined by comparing the baseline category to the worst case post-baseline category. PCI criteria is described in [Appendix 8](#).

- ***Hepatobiliary (Liver)***

Details of liver chemistry stopping criteria are described in the protocol.

Liver monitoring/stopping events will be summarized by treatment group.

Hepatobiliary laboratory abnormalities will be summarized by treatment group.

A scatter plot of maximum on-therapy ALT values versus baseline ALT values will be produced if larger data permit.

A scatter plot of maximum total bilirubin (xULN) versus maximum ALT (xULN) values on-therapy will be produced if larger data permit.

## 8.4. Other Safety Analyses

The analyses of non-laboratory safety test results including ECGs and vital signs will be based on GSK Core Data Standards, unless otherwise specified. The details of the planned displays are presented in [Appendix 10: List of Data Displays](#).

Endpoint / Parameter/ Display Type	Absolute			Change from BL		
	Summary		Individual	Summary		Individual
	T	F	L	T	F	L
ECG						
ECG Findings	Y		Y			
ECG Values by Visit			Y	Y		
Abnormal ECG Findings			Y			
Vital Signs						
Vital Signs by Visit	Y		Y	Y		
Worst Case Vital Sign Results Relative to PCI Criteria Post-Baseline Relative to Baseline	Y					
All Vital Signs for Subjects with Any Values of PCI			Y			
Ophthalmology						
Prior-Therapy Ophthalmologic Exams	Y		Y			
On-Therapy Ophthalmologic Exams	Y		Y			
Change in Anti-Hypertensive Medications						
Number (%) of Subjects Who Have Any Change in Anti-Hypertensive Medications During the Treatment Period	Y		Y			

### NOTES:

- T = Table, F = Figures, L = Listings, Y = Yes display generated, PCI = Potential Clinical Importance
- Summary = Represents TFL related to any summaries (i.e. descriptive statistics) of the observed raw data.
- Individual = Represents FL related to any displays of individual subject observed raw data.

### 8.4.1. Planned Other Safety Analyses Displays

- **ECG**

ECG findings ('normal', 'abnormal, not clinically significant', 'abnormal, clinically significant') will be summarized by assessment visit for each treatment group. Change from baseline in ECG values will be summarized using mean, standard deviation, minimum, median, and maximum by assessment visit for each treatment group. Findings without regard to visits (labelled "Worst Case Post-Baseline", only the worst case finding for each subject) will also be provided. All ECG measures (heart rate, PR interval, QRS duration, QT [uncorrected] interval and QTcB [calculated], result of ECG) will be included in listings.

- ***Vital Signs***

Vital sign values will be summarized using mean, standard deviation, minimum, median, and maximum by assessment visit for each treatment group. Separate summary statistics of pre- and post-dialysis vital signs will be provided for raw values and change from baseline. In a summary of change from baseline, each baseline value (i.e. pre- and post-dialysis baseline) will be used for calculation (Section 5.2).

The number of subjects with worst case vital sign results relative to PCI criteria which are post-baseline relative to baseline, including unscheduled assessments, will also be summarized by test and category by treatment group. The categories for PCI criteria are: To Low, To w/in Range or No Change, To High. The categorization is determined by comparing the baseline category to the worst case post-baseline category.

- ***Ophthalmology Exams***

The responses to each question and any questions will be summarized using number and percentage at each assessment visit by treatment group. The response will be classified into 'Yes' and 'No'. A summary of ophthalmology exams at screening and at on-therapy will be produced separately. The number and percentage of subjects with worst case after-screening ophthalmology exams (i.e., the response is 'Yes' at least once during whole treatment period, including unscheduled visits) will also be summarized by each question by treatment group.

- ***Change in Anti-Hypertensive Medications***

The number and percentage of subjects who have any change at least once in anti-hypertensive medications (type and/or dose) due to increased blood pressure during whole treatment period will be summarized by treatment group.

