5.2. Exclusion Criteria

Subjects meeting any of the following criteria must not be enrolled in the study.

Note: Verification at both provisional enrolment (screening) and official enrolment (Day 1) is required, unless otherwise specified.

Chronic kidney disease (CKD)-related criteria

1. Kidney transplant: Planned living-related kidney transplant during the study

Anemia-related criteria

- 2. Aplasia: History of bone-marrow hypoplasia or pure red cell aplasia
- 3. Other causes of anemia: pernicious anemia, thalassemia, sickle cell anemia, or myelodysplastic syndromes
- 4. Gastrointestinal (GI) bleeding: Evidence of actively bleeding gastric, duodenal, or esophageal ulcer disease OR clinically significant GI bleeding within 10 weeks prior to screening or during a period from screening to Day 1.

Cardiovascular disease-related criteria

- 5. Myocardial infarction, acute coronary syndrome, stroke, or transient ischemic attack: Diagnosed within 10 weeks prior to screening or during a period from screening to Day 1.
- 6. Heart failure: Chronic Class IV heart failure, as defined by the New York Heart Association (NYHA) functional classification system
- Corrected QT (QTc) Interval (screening verification only): QTc >500 msec; or QTc >530 msec in subjects with bundle branch block

Note: QT interval corrected using the Bazett's formula (QTcB) will be used, and ECG can be mechanically or manually read.

Other disease-related criteria

- 8. Liver disease (if any of the following occurs):
 - (Screening verification only): Alanine transaminase (ALT) >2×upper limit of normal (ULN)
 - (Screening verification only): Bilirubin >1.5×ULN (isolated bilirubin >1.5×ULN is acceptable if bilirubin is fractionated and direct bilirubin is <35%)

 Current unstable active liver or biliary disease (generally defined by the onset of ascites, encephalopathy, coagulopathy, hypoalbuminemia, esophageal/gastric varices, persistent jaundice, or cirrhosis)

CONFIDENTIAL

- Note: Stable liver disease (including asymptomatic gallstones, chronic hepatitis B/C, or Gilbert's syndrome) is acceptable if the subject otherwise meets entry criteria..
- 9. Malignancy: History of malignancy within 2 years prior to screening, currently receiving treatment for cancer, or complex kidney cyst >3 cm (II F, III or IV based on the Bosniak classification)

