6.9. Treatment of Study Treatment Overdose

For the purposes of this study, an overdose of daprodustat is defined as any dose greater than the highest daily dose included in the protocol. There is no specific antidote for overdose with daprodustat. The expected manifestations of daprodustat overdosage include signs and symptoms associated with an excessive and/or rapid increase in Hgb concentration. Daprodustat is highly protein bound; thus, clearance of unchanged daprodustat by hemodialysis or peritoneal dialysis is very low and these are not effective methods to enhance the elimination of daprodustat. Daprodustat metabolites are, in part, cleared via hemodialysis. In the event of a suspected overdose, it is recommended that the appropriate supportive clinical care be instituted, as dictated by the subject's clinical status. Additionally, subjects should be monitored closely for cardiovascular events, increased heart rate and hematologic abnormalities.

Consult the respective approved Prescribing Information for information on overdose for darbepoetin alfa.

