7.4.6. Electrocardiogram (ECG)

12-lead ECGs will be recorded in supine position. The heart rate, PR, QRS, and QT (pre-corrected) intervals will be measured. QTcB should be calculated by machine or manually by designated staff at each site. The investigator determines whether the ECG data is assessable or not. Measurement method and measurement timing (i.e., before or after dialysis) should be consistent as far as possible during the study period.

At Screening visit when an ECG is performed, two additional ECGs are required if initial ECG indicates prolonged QTc. The average QTcB value of all three ECGs will be used to determine eligibility.

QTc exclusion criteria can be found in Section 5.2. Refer to SRM for further details.

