9.4.4.3. Other Safety Parameters

For laboratory tests, vital signs and ECG, parameters and/or changes from baseline will be summarized using summary statistics at each assessment visit. The number and percentage of subjects with values of the potential clinical importance values will be tabulated. The criteria for the potential clinical importance will be described in the RAP. For lipid parameters (total cholesterol, LDL cholesterol, and HDL cholesterol), percent changes will also be tabulated. The number (%) of subjects who have any change in anti-hypertensive medications (type and/or dose) due to increased blood pressure will be tabulated.

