**15.8.2. Vital Signs**

Vital Sign Parameter (Absolute)	Units	Clinical Concern Range	
		Lower	Upper
Systolic Blood Pressure	mmHg	< 85 mmHg	> 180 mmHg
Diastolic Blood Pressure	mmHg	< 45 mmHg	> 110 mmHg
Heart Rate	beats/min	< 40 beats/min	> 110 beats/min

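### The protocol promises counts of subjects with ECG values of potential clinical importance; the SAP sets no ECG criteria, plans no such table and does not record the change

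*SAP*

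**What the plan says.** Protocol 9.4.4.3 (Other Safety Parameters) puts ECG in scope: "For laboratory tests, vital signs and ECG, parameters and/or changes from baseline will be summarized using summary statistics at each assessment visit". The same paragraph continues: "The number and percentage of subjects with values of the potential clinical importance values will be tabulated". It then passes the definition to the analysis plan: "The criteria for the potential clinical importance will be described in the RAP". ECG is not exempted.

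SAP Appendix 8 holds those criteria in two parts: 15.8.1 for laboratory values and "15.8.2. Vital Signs", where the parameters are systolic pressure, diastolic pressure and heart rate. There is no ECG part.

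SAP 8.4.1 plans three things for ECG. The first is the overall reading in three grades (normal, and abnormal with or without clinical significance), by visit and as each subject's worst post-baseline grade. The second is change in the numeric measures: "Change from baseline in ECG values will be summarized using mean, standard deviation, minimum, median, and maximum by assessment visit for each treatment group". The third is subject listings of heart rate, PR, QRS, uncorrected QT and QTcB. Appendix 10 has two ECG tables, 3.43 (findings) and 3.44 (change from baseline).

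On collection, Protocol 7.4.6 states: "The heart rate, PR, QRS, and QT (pre-corrected) intervals will be measured". It has sites calculate QTcB. The only numeric QTc limit in either document is the screening exclusion in Protocol 5.2: "QTc >500 msec; or QTc >530 msec in subjects with bundle branch block".

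**The concern.** A count that the protocol commits to has no definition and no output in the SAP, and nothing tells the reader that it was dropped. ECG is a named safety endpoint in both documents.

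A QTc safety signal may lie in a few subjects with large values. Summary statistics of change are a poor way to see how many there are: the mean dilutes them, and the maximum describes one subject. If a cluster of long QTc values arose in one arm, a reader of the planned tables could not give its size or compare it with the other arm without counting by hand from the listings.

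**Working it through.** **Step 1. Promise against delivery.** The plan states no figure to reproduce, so this is a comparison of text.

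| Domain in Protocol 9.4.4.3 | Criteria in SAP Appendix 8 | PCI table in SAP Appendix 10 |
|---|---|---|
| Laboratory tests | 15.8.1 | 3.28, 3.32, 3.36, 3.40 |
| Vital signs | 15.8.2 | 3.47 |
| ECG | none | none |

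SAP Table 1 has one row, on multiplicity. The SAP revision history does not mention ECG. Protocol Section 9 requires departures from its analyses to be documented in the RAP or the final study report; the RAP does not do so here.

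**Step 2. What the planned ECG displays can show.** In the SAP 8.4 display grid, ECG values by visit have a listing but no summary table on the absolute scale; the only numeric table is of change. A maximum change of +65 msec could be 380 to 445 msec or 440 to 505 msec, and the table cannot tell these apart. Table 3.43 counts subjects by overall reading, but the documents attach no numeric QTc rule to that grading.

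**Step 3. How far a cluster moves the mean.** Inputs: 135 randomized per arm (Protocol 9.2.1), and 202 expected completers (Protocol 4.3), that is 101 per arm. Assumptions, because the documents give no on-study QTc data: k = 5 subjects with +60 msec each, and an SD of change of 20 to 30 msec.

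- Shift of the arm mean = 60 × k / n. For n = 135: 60 × 5 / 135 = 2.2 msec. For n = 101: 60 × 5 / 101 = 3.0 msec.
- Standard error of the between-arm difference = SD × √(2/n). For n = 135: 20 × √(2/135) = 2.4 to 30 × √(2/135) = 3.7 msec. For n = 101: 2.8 to 4.2 msec.

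The shift is about one standard error or less, so the mean would not reveal such a cluster. The maximum would flag one member of it.

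**Step 4. QTcB as the only correction.** Assume that QT follows the cube-root relation with constant QTcF. Then QT = QTcF × (60/HR)^(1/3) and QTcB = QT / (60/HR)^(1/2), so QTcB = QTcF × (HR/60)^(1/6). With QTcF = 420 msec:

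| Heart rate (bpm) | QTcB (msec) | Change from 70 bpm (msec) |
|---|---|---|
| 65 | 425.6 | −5.3 |
| 70 | 430.9 | 0 |
| 75 | 435.9 | +5.0 |
| 80 | 440.6 | +9.7 |

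Over QTcF 400 to 440 msec and a starting rate of 60 to 80 bpm, a 5 bpm rise gives +4.3 to +5.9 msec and a 5 bpm fall gives −4.5 to −6.3 msec. The distortion follows the sign of the heart-rate change.

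**The case against.** The strongest reply is that the ECG analysis is fuller than a complaint about missing counts suggests. A reader might infer that QT is analysed only as a mean change; SAP 8.4.1 does not support that. It also gives SD, minimum, median and maximum, counts overall readings including the worst per subject, and lists every value. A single subject rising by 100 msec would appear as a maximum of +100 in Table 3.44, if QTcB is among the values tabulated there. This stands, and it narrows the gap to absolute QTc and threshold counts.

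Second, the protocol leaves the criteria to the RAP, and SAP 15.8 is selective even for laboratory tests: creatinine, glucose and chloride are measured but have no row. So a missing row for one parameter is not in itself a departure. That is fair, but here a whole named domain is absent without explanation.

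Third, a reader might infer that Bazett correction is an SAP failing that will make a heart-rate difference look like QT prolongation. The documents do not support this either. QTcB is the protocol's own choice (5.2 and 7.4.6). Neither document reports a between-arm heart-rate difference. The heart-rate remark in Protocol 6.9, "subjects should be monitored closely for cardiovascular events, increased heart rate and hematologic abnormalities", concerns suspected overdose. Vital-sign heart rate is summarized by arm, so a difference would be seen. The figures in Step 4 hold only under the assumed cube-root relation, and a lower rate would shorten QTcB and could hide prolongation.

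Fourth, QT prolongation is not an event of special interest, post-baseline ECGs are scheduled only at Weeks 24 and 52, and arrhythmias are captured on the cardiovascular event page and in patient profiles. This limits the stakes but does not remove the commitment in 9.4.4.3.

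**Conclusion.** The point holds as a reporting gap. As written, the SAP does not deliver the ECG count that Protocol 9.4.4.3 promises and does not declare the change. The planned displays show the largest single change and the overall readings, but not absolute QTc or the number of subjects beyond a numeric limit.

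The size of any consequence cannot be computed from the documents. The 2.2 to 3.0 msec shift illustrates dilution and rests on the assumed cluster and SD. Sole reliance on QTcB is a conditional, secondary matter: it could distort the comparison in either direction if heart rate differed between arms, which nothing in the documents shows. The primary and principal secondary efficacy analyses are unaffected.

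**What to change.** 1. Add ECG rows to SAP 15.8 with pre-specified QTcB reporting cutoffs. The protocol's screening limits (>500 msec; >530 msec with bundle branch block) are available as descriptive cutoffs; they would not be a management rule. On-study values would not be fully like-for-like with screening, where a prolonged QTc is averaged over three ECGs. State whether heart rate, PR and QRS from the ECG also get criteria. If bundle branch block status is not in the database, show both limits for all subjects.
2. Add one table to SAP 8.4 and Appendix 10: n (%) of subjects above each cutoff, by arm, by visit and worst post-baseline, with the number of subjects with an ECG as denominator.
3. If the sponsor prefers not to tabulate ECG values this way, record and justify the omission in SAP Table 1.
4. Optional: derive QTcF from the recorded QT and heart rate and show it beside QTcB in Table 3.44. QTcF is already in the SAP abbreviation list but is used in no analysis.

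Cost: SAP wording, one extra table and, if item 4 is taken up, one derivation. No new procedure or data collection is needed.

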7.4.8. Ophthalmology

Ophthalmology exams will be performed by a study-designated ophthalmology specialist. Each assessment will include a comprehensive eye exam with at least the following components: measurement of best corrected visual acuity, intraocular pressure, an anterior chamber exam, and a fundoscopic exam. These exams will be used for assessment of ocular adverse events. Assessment results will be captured on worksheets which will be transferred to the eCRF. Additional details on the process for completing these assessments are provided in the SRM.

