Proliferative retinopathy, macular edema, choroidal neovascularization	Small increases in cardiac troponin in 6 month rat study were consistent with the background finding of spontaneous rodent cardiomyopathy. There were no elevations observed in cardiac troponin in 9 month monkey study. Cardiomyopathy has not been associated with naturally occurring mutation in man which results in increased HIF stabilization. ECHO assessments performed in phase 2b studies (24 weeks treatment duration) did not identify any clinically meaningful changes in LVEF. Following review of clinical data received to date, this has not been identified as a safety concern for daprodustat. Increases in local (ocular) VEGF production with retinal neovascularization and macular edema observed in diabetic retinopathy and to choroidal leakage, edema and neovascularization seen in age-related macular degeneration (Campochiaro, 2006). Administration of 60 mg/kg daprodustat to mice caused minimal increases in circulating VEGF while significant EPO increases were observed. No ocular abnormalities were seen in non-clinical studies of up to 13 weeks duration in mice and dogs, 26 weeks in rats, and 39-weeks in monkeys. In clinical studies up to 4 weeks duration, a dose-ordered increase in VEGF plasma concentrations was observed at doses ranging from 10 to 150 mg. In studies up to 24 weeks duration at doses up to 25 mg, changes in VEGF plasma concentrations were variable but similar relative to control. Ophthalmologic assessments performed in phase 2b studies (24 weeks treatment duration) did not identify any clinically meaningful changes in proliferative retinopathy, macular	 Ophthalmology exams will be performed during screening, at approximately Week 12 on-study, and at the end of treatment. These risks have been identified as AEs of special interest and will be monitored instreamly by the internal safety review team throughout the study period. Suspected proliferative retinopathy, macular edema, choroidal neovascularization or symptoms consistent with these events should be investigated by ophthalmologic consultation as clinically warranted.
	edema, or choroidal neovascularization. Following review of clinical data received to date, this has not been identified as a safety concern for daprodustat.	
Exacerbation of rheumatoid arthritis	In inflamed rheumatic joints, activation of HIF- related genes	These risks have been identified as AEs of special

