12.6.1. Definition of Adverse Events

Adverse Event Definition:

- An AE is any untoward medical occurrence in a patient or clinical investigation subject, temporally associated with the use of a medicinal product, whether or not considered related to the medicinal product.
- NOTE: An AE can therefore be any unfavorable and unintended sign (including an abnormal laboratory finding), symptom, or disease (new or exacerbated) temporally associated with the use of a medicinal product.

Events meeting AE definition include:

- Any abnormal laboratory test results (hematology, clinical chemistry, or urinalysis) or other safety assessments (e.g., ECGs, radiological scans, vital signs measurements), including those that worsen from baseline, and felt to be clinically significant in the medical and scientific judgement of the investigator.
- Exacerbation of a chronic or intermittent pre-existing condition including either an increase in frequency and/or intensity of the condition.
- New conditions detected or diagnosed after study treatment administration even though it may have been present prior to the start of the study.
- Signs, symptoms, or the clinical sequelae of a suspected interaction.
- Signs, symptoms, or the clinical sequelae of a suspected overdose of either study treatment or a
 concomitant medication (overdose per se will not be reported as an AE/SAE unless this is an
 intentional overdose taken with possible suicidal/self-harming intent. This should be reported
 regardless of sequelae).
- "Lack of efficacy" or "failure of expected pharmacological action" per se will not be reported as an AE or SAE. However, the signs and symptoms and/or clinical sequelae resulting from lack of efficacy will be reported if they fulfil the definition of an AE or SAE.

Events **NOT** meeting definition of an AE include:

- Any clinically significant abnormal laboratory findings or other abnormal safety assessments
 which are associated with the underlying disease, unless judged by the investigator to be more
 severe than expected for the subject's condition.
- The disease/disorder being studied or expected progression, signs, or symptoms of the disease/disorder being studied, unless more severe than expected for the subject's condition.
- Medical or surgical procedure (e.g., endoscopy, appendectomy): the condition that leads to the procedure is an AE.
- Situations where an untoward medical occurrence did not occur (social and/or convenience admission to a hospital).

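### A cheap improvement, not an error: the worst-case eye row counts any later 'Yes' without the subject's own screening answer, so if 'Yes' means 'finding present', new findings are hard to see in the summary

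*SAP*

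**What the plan says.** The Ophthalmology Exams paragraph of SAP 8.4.1 classifies each answer as 'Yes' or 'No' and tabulates answers by visit and arm. It then says: "A summary of ophthalmology exams at screening and at on-therapy will be produced separately". The worst case after screening is defined, per question and arm, as "the response is 'Yes' at least once during whole treatment period, including unscheduled visits".

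The display list in SAP 15.10.4.4 has two eye tables, 3.48 (screening) and 3.49 (on therapy). Neither title mentions a comparison within subjects. The paragraph does not name the table that will hold the worst-case row. Table 3.49 is the natural reading, but its shell (SAFE_T7) is not available, because SAP 15.11 keeps the shells in separate documents.

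Practice elsewhere in the SAP is mixed. For worst-case vital signs, SAP 8.4.1 says: "The categorization is determined by comparing the baseline category to the worst case post-baseline category". SAP 8.3.1 applies the same rule to laboratory results. The ECG worst case has no such reference; it uses "only the worst case finding for each subject".

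The data for a comparison will exist. Protocol Appendix 2 says: "Ophthalmology exams will be performed during screening, at approximately Week 12 on-study, and at the end of treatment".

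**The concern.** Ophthalmology assessments are a named safety endpoint, retinal and choroidal events form a category of adverse events of special interest (AESI), and Tables 3.48 and 3.49 are both in the headline package (SAP 15.10.3). A reader will look to Table 3.49 for eye findings that appeared on treatment.

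An any-'Yes' count cannot separate a finding that appeared on treatment from one already there at screening. Existing findings are plausible: Protocol 5.2 has no eye-disease exclusion, the re-screening footnote to Protocol Table 10 allows for screening exams with findings, and history of diabetes is a planned subgroup (SAP 5.4.2). If such findings are common and are recorded again, most of the row could describe subjects as they entered the trial. Chance differences between arms at entry would then pass straight into it.

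What is at stake is the readability of one descriptive safety display.

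**Working it through.** The documents state no figure for the eye displays, so there is none to reproduce. The calculation shows only how the two ways of counting differ.

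**Inputs**
- n = 135 per arm (Protocol 4.3), all examined. Alternative: 101 per arm, half of the 202 expected completers.
- Assumed, with no source in the documents: 'Yes' means present; the same questions are asked at both times; screening prevalence p = 30% (range 10% to 40%); share of screening findings recorded again r = 1 (alternative 0.5); new findings i = 6% vs 2% among subjects clear at screening.

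**Formulas**
- Planned row, rate per arm: p·r + (1 − p)·i. With rates a and b in the two arms, SE of the difference = √[(a(1 − a) + b(1 − b))/n].
- No-to-Yes row: rate i among m = n(1 − p) subjects per arm, with the same SE formula and m in place of n.

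**At p = 30%, r = 1**
- Planned: 0.30 + 0.70 × 0.06 = 34.2% and 0.30 + 0.70 × 0.02 = 31.4%. Difference 2.8 points, ratio 1.09. SE = √[(0.2250 + 0.2154)/135] = 5.7 points.
- No-to-Yes: 6% vs 2% of m = 135 × 0.70 = 94.5. Difference 4.0 points, ratio 3.0. SE = √[(0.0564 + 0.0196)/94.5] = 2.8 points.
- Expected excess of subjects: 135 × 0.028 = 3.8 and 94.5 × 0.04 = 3.8, the same in both rows. Its SD is 135 × 0.0571 = 7.7 in the planned row. In the No-to-Yes row it is √[135 × (0.042 × 0.958 + 0.014 × 0.986)] = 2.7.
- Source of the extra noise: the chance difference between arms in screening prevalence has SD √(2 × 0.30 × 0.70/135) = 5.6 points.
- Chance that the arm with the higher true rate shows the lower observed percentage (simulation, 400,000 draws): about 29% planned, 7% No-to-Yes.

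**Range over prevalence (n = 135, r = 1, 6% vs 2%)**

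| p | Planned difference (SE), points | Planned ratio | No-to-Yes difference (SE), points |
|---|---|---|---|
| 10% | 3.6 (4.2) | 1.31 | 4.0 (2.5) |
| 20% | 3.2 (5.1) | 1.15 | 4.0 (2.7) |
| 30% | 2.8 (5.7) | 1.09 | 4.0 (2.8) |
| 40% | 2.4 (6.0) | 1.06 | 4.0 (3.1) |

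**Other assumptions**
- r = 0.5: planned SE 3.4, 4.1, 4.7 and 5.1 points at the four prevalences.
- 101 per arm, p = 30%, r = 1: SE 6.6 vs 3.3 points.
- New findings 3% vs 2%, p = 30%, r = 1: planned difference 0.7 points, SE √[(0.2180 + 0.2154)/135] = 5.7; No-to-Yes difference 1.0 point, SE √[(0.0291 + 0.0196)/94.5] = 2.3. Neither display is informative at that size.
- p = 0: the two counts are identical.

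**The case against.** The strongest objection is that the exams already serve their stated purpose by another route. Protocol 7.4.8 says: "These exams will be used for assessment of ocular adverse events". The adverse event definition covers abnormal safety assessments "including those that worsen from baseline" and flare-ups of existing conditions, and AESIs are selected case by case before unblinding. The headline package also carries the screening table, the AESI table and listing, and Listing 64 with each subject's exams. Chance imbalance at screening is therefore visible, and a subject-by-subject check is possible. This stands, and it is why the point is minor. It does not make the table redundant: adverse event reporting depends on the investigator's judgement of clinical significance, Table 3.48 gives only group-level rates, and Listing 64 leaves the comparison to be made by hand.

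Second, the point depends on material that is not available. If the on-therapy questions ask about new or worsened findings, nothing is lost, and a No-to-Yes table would compare different questions. It would also move true worsening in subjects with existing eye disease out of its main row. This stands too, so the recommendation is limited to questions asked in the same form at both times.

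Third, the assumed tripling has no support; Protocol Appendix 2 reports no clinically meaningful eye changes in the phase 2b studies. The plan also calls for no ratio or test on this row. Both are correct, and the figures above are illustration only.

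A reader might also infer that the blank change-from-baseline cells beside "On-Therapy Ophthalmologic Exams" in the SAP 8.4 overview prove that no comparison is planned. They do not. The baseline-relative worst-case vital-sign row in the same overview, and the worst-case laboratory rows in SAP 8.3, also have those cells blank. The evidence is the text of SAP 8.4.1 and the list of table titles.

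**Conclusion.** The point holds as a minor, conditional improvement. The planned worst-case eye row ignores the subject's screening answer, and no listed table makes that comparison. If 'Yes' means 'finding present' and the questions are the same at both times, existing findings add noise and make new ones hard to see. In the illustration the standard error of the difference is 5.7 points against 2.8, and over prevalences of 10% to 40% it is 4.2 to 6.0 against 2.5 to 3.1. The size rests wholly on assumed prevalence, persistence and incidence. If the questions already ask for new or worsened findings, there is no loss.

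A reader might infer more: that the row is biased, that ocular harm would go unreported, or that the SAP breaks its own rule. The documents support none of these. Randomisation balances existing findings in expectation, and the expected excess is the same 3.8 subjects under either count. New or worsened harm also reaches the AE and AESI tables. The ECG worst case is counted in the same unshifted way, so there is no single convention to break. Efficacy inference, alpha and sample size are unaffected.

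**What to change.** First check the wording of the eye questions on the worksheet or eCRF. If the on-therapy questions already ask for new or worsened findings, no table is needed; a footnote to Table 3.49 saying so would be enough.

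Otherwise keep the any-'Yes' row and, for questions asked in the same form at screening and on therapy, add one descriptive table. By arm and question, it cross-tabulates the screening answer against the worst later answer. It gives the count and percentage going from 'No' to 'Yes' among subjects with 'No' at screening and at least one later exam, and shows subjects with 'Yes' at screening as their own row.

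The cost is one extra table from data already collected. The denominator of the new-finding row is smaller (94.5 instead of 135 per arm at 30% prevalence). Worsening of an existing finding will still be seen only through the AE and AESI tables.
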